Stable isotope administration will begin the night of the admission; glucose appearance, fractional gluconeogenesis and glycerol turnover will be measured with [6,6²H₂]glucose, deuterated water [²H₂O], [¹³C₁₆]potassium palmitate and [²H₅]glycerol respectively. Lean body mass (LBM) measurements from dual x-ray absorptiometry scans will be used to calculate the isotope administration rates. Deuterated water (3 gram•kg_{LBM}) will be administered in 3 divided doses at 9pm, 12am, and 3am. Primed (60×the minute infusion rate) and continuous infusions of [6,6²H₂]glucose and [²H₅]glycerol will start at 4am (t= -240m) and continue until 9am (t= 0m). At 730am, an unprimed [¹³C₁₆] palmitate infusion will be started. At 9am (t= 0m), the glycerol and palmitate infusions will be discontinued. The [6,6²H₂]glucose infusion will continue until 2pm (300m) to quantify gluconeogenesis during meal absorption using a continuous feeding protocol with a nutrient drink and [6,6²H₂]glucose intravenous infusion will be used to mimic the steady-state prandial state^{70,71}. At 9am (t= 0m), participants will be fed a lactose-free nutrient drink to provide ~50% of estimated total energy needs and macronutrient composition that matches the previous days' meals in equal portions every 30 minutes over the 5h

of feeding. The purpose of this feeding strategy is to evaluate the acute response to refeeding, and not to provide full caloric requirements⁷¹. Isotope enrichment will be measured over a period of 30 minutes during steady state. Therefore, blood samples for steady-state conditions will be obtained at the following time periods: (1) fasting between 830-9am (t= -30 to 0m) and (2) prandially between 130-200pm (t=270 to 300m). Blood samples for hormones and metabolites (including glucose, insulin, incretins in protease inhibitor treated tubes) will be collected every 30 minutes between 9am and 2pm. Whole blood will be centrifuged and plasma transferred and frozen at -80C until analyses.

c. Urine collection

A timed 24-hour urine collection to measure urinary nitrogen will start at noon on admission and continue until noon on the study day. Total daily urinary nitrogen excretion will be used to determine the total body glucose and lipid oxidation rates as previously described⁷².

d. Indirect calorimetry

To calculate substrate oxidation, indirect calorimetry (hood) will be performed for 30-45 minutes between 7-8am, and 1-2pm to measure oxygen consumption and carbon dioxide production rates.

e. Stool Sample

A research stool sample will be collected at home and brought to the visit or collected during the admission. The stool sample will be stored at 4C in a sterile plastic vial and processed within 24 hours of collection.

f. Side-effect Questionnaire

Questionnaires will be completed by the participants at the study visit (Appendix A)

g. Blood glucose monitoring

Blood glucose will be monitored with either fingerstick blood glucose twice daily (fasting and bedtime) or by using an FDA- approved continuous glucose monitoring device (CGM) (for example, the Dexcom® CGM System). The device will be used to monitor glucose in real-time, approximately every 5 minutes. The system consists of a small sensor, transmitter, and hand-held receiver. The small sensor, with a small needle attached, will be inserted subcutaneously. The transmitter, which is attached to the sensor, will send the measured glucose to the receiver. The sensor is changed per manufacturer recommendations. Participants will receive training on removing and replacing the sensor and education on the signs and symptoms of hyperglycemia see Appendix B. All CGM or glucometer supplies will be provided by the study team.

Visit 3 and 4: Follow-up Outpatient Visit

Participants will return to the NIH CC clinic for an outpatient follow-up visit. Visit 3 will occur between 4-5 weeks and Visit 4 will occur between 8-9 weeks. The procedures at Visit 3 and 4 will be identical, and are outlined as follows:

1. Blood glucose records and glucometers will be reviewed.
2. Pill and pen counts performed by the study staff.
3. Blood and urine samples will be collected for glucose and metformin monitoring (including hemoglobin A1c, metformin concentrations).
4. We will review medication adherence and tolerance and emphasize compliance with study visits.
5. A research stool sample will be collected at home and brought to the visit or collected during the admission. The stool sample will be stored at 4C in a sterile plastic vial and processed within 24 hours of receipt.
6. We will collect questionnaire to assess side effects after starting the medication or changing dose. The sample questionnaire is in Appendix A.

Visit 5: Final Tracer Study

Participants will return for an inpatient tracer visit protocol after 12 weeks \pm 14 days on study medication. Participants will receive their last dose of study medication at supper in the evening of admission Day 1 during Visit 5.

Visit 5 procedures will be identical to Visit 2 above with the following additional blood sampling for metformin concentrations. To measure blood (plasma and RBC) plasma samples for metformin for participants within the study receiving metformin at doses 1000-2000mg daily. Samples for metformin analysis (3ml of whole blood) will be collected, processed for isolation of plasma and RBC and frozen at -80C until analysis during the OGTT as follows:

- a) Day 1 during the OGTT at time 0, 0.5h, 1h, 1.5h, 2h, 3h 4h, 6h, 8h and 8pm (pre-second dose).
- b) Day 2 at 8am and at 2pm

After completion of Visit 5, participants will be instructed to resume their home medication regimen.

Study Agents/ Intervention

Two study agents will be used: metformin oral 500mg oral tablet and liraglutide (6mg/ml, 3ml) solution for subcutaneous injection, pre-filled, multi-dose pen that delivers doses of 0.6mg, 1.2mg or 1.8mg. Both metformin and liraglutide will be used within the approved dosing regimens. Neither drug will be altered from the approved dosage formulation. Table 3 illustrates the titration schedule for each study drug.

Table 3: Titration Schedule for Metformin and Liraglutide

Study schedule	Week	Liraglutide (subcutaneous injection)	Metformin (oral tablet)
Run-in	-1 to 0	-	-
After baseline visit	0-1	0.6mg once daily	500mg once daily
	1-2	1.2mg once daily	500mg twice daily
Target study dose	3-12	1.8mg once daily	1000mg twice daily

The participant will start the study drug(s) on Day 2 of Visit 2, after the tracer protocol is completed. The PI will review blood glucose logs and/ or CGM readings weekly and ensure that the study drug(s) titrated to the highest tolerable dose as guided by Table 3 above. For patients on combination therapy, the dose of liraglutide will not be increased if the fasting blood glucose is <75 mg/dl on 2 or more consecutive days. If the fasting blood glucose subsequently rises to ≥90 mg/dl on 2 or more consecutive days, the dose of liraglutide will increase by 0.6mg once daily every 5-7 days to achieve maximum tolerable dose.

Dose titration for gastrointestinal intolerance

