The primary objective of this pilot study is to compare the ability of two anti-diabetic regimens (metformin and liraglutide versus metformin alone) to lower gluconeogenesis (glucose produced by the liver) in African-American youth with type 2 diabetes. The secondary objectives are to evaluate the effect of these regimens on the following: (1) hepatic glucose production, and insulin sensitivity and (2) insulin and gut hormones concentrations (e.g. incretins). In addition, we will examine the relationship of known differences in genes associated with metformin transport and action with changes in gluconeogenesis and begin to explore the role of gut bacteria to metformin's glucose-lowering effect.

The study design is a parallel-randomized intervention trial of African-American youth with type 2 diabetes who are not on insulin therapy and who are within 5 years of diagnosis. Patients aged 12- 25 years with type 2 diabetes will be enrolled. Participants will be randomized into two intervention arms (16 in each group): metformin and liraglutide versus metformin alone. The study will consist of 5 visits. At Visit 1, a medical history, physical examination and screening labs will be done. Then the eligible participants will undergo a one-week drug-free run-in. At Visit 2 there will be an overnight inpatient stay to perform metabolic testing prior to starting the study drug(s). Participants will start the study drug(s) immediately after Visit 2 and remain on the study drug(s) for 12 weeks. Follow-up monitoring will be performed at 4-week intervals (Visit 3 and 4). The final visit (Visit 5) will occur after 12 weeks.

The ultimate goal of this multi-site project is to begin to address diabetes disparities in African-American youth by understanding the mechanism of action of these diabetes agents to inform precision medicine initiatives. This project brings together the skills and expertise of investigators within the National Institute of Diabetes and Digestive Disorders

and Kidney Diseases (NIDDK), the National Human Genome Research Institute (NHGRI), and the Children's National Medical Center (CNMC). Patient recruitment and data collection will occur at NIH Clinical Center. Eligible patients may be identified through CNMC but no enrollment, informed consent or study visits will occur at CNMC.

Introduction and Significance

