- a) The change in the gut microbial composition and distribution in African-American youth with type 2 diabetes after 12 weeks of metformin.

Metformin response and pharmacokinetic-pharmacodynamic model

- b) Construct a pharmacokinetic-pharmacodynamic model based on plasma and RBC metformin concentrations, and treatment outcome response (including change in glucose production, gluconeogenesis, incretin concentrations).

Study Design and Methods

Study Design

This is a pilot randomized parallel design study of African-American youth with type 2 diabetes who are not on insulin therapy, with two intervention arms (combination therapy with metformin and liraglutide, and metformin alone).

Participants enter 5-7 day drug-free run-in period prior to initial metabolic evaluation. Participants will be evaluated before and after 12 weeks of study drug(s).

Randomization

The NIH Clinical Center (CC) Pharmacy will perform block randomization stratified by sex. Randomization will be stratified by sex with a block size of 6. The randomization schedules will be constructed by an independent statistician and shared with the NIH CC Pharmacy. The PI and study staff will not view the randomization schedule *a priori*. Subjects will be randomized as they enter the protocol as follows: The PI or study staff will notify the NIH CC pharmacy of the eligible enrolled participant and the pharmacy will assign the intervention arm according to the predetermined randomization schedule. All participant data will be entered into a NIDDK RedCap® database and the participant will be randomized consecutively using the single randomization list maintained by the NIH CC Pharmacy.

Study Protocol

Figure 1 illustrates the study design in which there will be 5 study visits: Visit 1 (screening outpatient), Visit 2 (tracer inpatient), Visit 3 and 4 (follow-up outpatient) and Visit 5 (tracer inpatient). Eligible patients may be identified at CNMC but no study visits will occur at CNMC.

[figure not shown]

Figure 1 –Study Design: randomized 12-week two-treatment arm clinical trial

Visit 1: Screening Outpatient Visit

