This visit is designed to explain the protocol to the participant and their parents, determine participant eligibility, provide study protocol details to the family, and obtain informed consent and assent. Each participant will undergo a history and physical examination, routine blood work (including lipase and amylase) and pregnancy test to determine eligibility. Youth will meet with a member of the nutrition team to discuss your diet and to be educated on keeping 3-day food records before Visit 2 and 5 and will discuss metabolic diet selection during the inpatient stay. In addition, the dietitian will perform body measurements including waist, hip and neck circumferences, those measurements will take only few minutes and are not painful.

Education and Blood glucose monitoring during the run-in period

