All participants will be seen by a nutritionist and counseled on standard diabetes management, diet and lifestyle management. Participants will be asked to discontinue all anti-diabetic medications for the 5-7 days preceding Visit 2. This drug-free period is necessary to assess the participant's metabolic response off of anti-diabetic medications. During the drug-free period and throughout the study, youth will monitor their blood glucose either by fingerstick blood glucose (FSBG) at least twice daily or they will wear a continuous glucose monitoring (CGM) device. Participants who do not have their own glucometer will be provided with glucose-monitoring devices and supplies and educated on their use. The CGM supplies will be provided by the study team and all participants will receive instruction on how to wear and use the CGM device. All individuals will be closely monitored during the drug-free run-in period with 2-3 times daily blood glucose checks via home glucose monitoring and daily check-in reports by study staff. If severe hyperglycemia, FSBG is >200mg/dl fasting or 300mg/dl pre-dinner, is noted during the run-in period, they will notify the study PI immediately. To monitor participants with elevated FSBG the physician may recommend admission to the NIH metabolic unit prior to Visit 2. Individuals with persistently elevated FSBG and/ or signs and symptoms of metabolic decompensation (e.g. vomiting, dehydration, lethargy, abdominal pain, ketonuria and acidosis) will be withdrawn from the study and restarted on his/ her medication. During the drug-free run-in period, individuals who cannot wear the CGM device or complete fingerstick blood glucose measures or who cannot be reached for ≥ 3 days during this period, will be withdrawn from the study.

Visit 2: Baseline Tracer Inpatient Visit

Visit 2 will take place ~ 1-2 weeks after the screening visit. All participants will be admitted to the Metabolic Research Unit at the NIH for an overnight tracer visit to measure indices of glucose and lipid metabolism, energy expenditure and obtain samples for genetic analysis prior to initiation of the study drugs. The tracer protocol is illustrated in Figure 2 and outlined below:

- Admission, oral glucose tolerance test (OGTT) and Dual x-ray absorptiometry (DXA) scan
- Stable isotope administration and steady state labs
- Urine collection
- Indirect calorimetry

[figure not shown]

Figure 2 –Study Protocol for Overnight Tracer Visits

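### The randomisation trigger, read literally, assigns the arm before the drug-free run-in and baseline tracer; it should be moved to after the Visit 2 tracer and before first dispensing

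*Combined protocol and SAP*

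**What the plan says.** All references are to the combined protocol and SAP.

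- **Randomization.** "Subjects will be randomized as they enter the protocol as follows". The procedure that follows is: "The PI or study staff will notify the NIH CC pharmacy of the eligible enrolled participant and the pharmacy will assign the intervention arm". No visit or day is named. Before assignment, "The PI and study staff will not view the randomization schedule"; the section does not say who learns the arm afterwards, or when.
- **Visit 1: Screening Outpatient Visit.** The visit serves, among other things, to "determine participant eligibility, provide study protocol details to the family, and obtain informed consent and assent". Randomisation is not listed there or under any other visit.
- **Précis.** After Visit 1: "Then the eligible participants will undergo a one-week drug-free run-in".
- **Study Design.** "Participants enter 5-7 day drug-free run-in period prior to initial metabolic evaluation".
- **Education and Blood glucose monitoring during the run-in period.** Participants who do not complete glucose monitoring, or "who cannot be reached for ≥ 3 days during this period, will be withdrawn from the study". Persistent hyperglycaemia and metabolic decompensation are also grounds for withdrawal.
- **Study Agents/ Intervention.** "The participant will start the study drug(s) on Day 2 of Visit 2, after the tracer protocol is completed". Under Dispensing and Storing Study Medications, the first supply is handed out at the end of Visit 2.
- **Analysis of Primary and Secondary Outcomes.** The randomised groups are compared on change in gluconeogenesis, adjusted for baseline. No analysis set is defined, and there is no rule for participants without a baseline.

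**The concern.** The arm is not needed until study drug starts on Day 2 of Visit 2. Before then come a run-in with several withdrawal rules and the baseline measurement on which the primary outcome depends. If assignment takes place at entry, two things follow.

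First, run-in withdrawals become post-randomisation exclusions. They have no baseline tracer and no treatment, so a baseline-adjusted change analysis cannot use them, and they draw on an attrition allowance of only 4 per arm.

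Second, one arm adds an injection and no placebo is described. If the arm is disclosed on assignment, staff could decide on run-in withdrawal knowing it, and families could leave because of it. Some of these decisions need judgement: no duration is given for persistently elevated glucose. The run-in monitoring section also joins that criterion to decompensation signs with and/or, whereas the section on run-in risks requires both. Those two passages must be reconciled.

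**Working it through.** **Step 1: the order of events.**

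| Event | Where placed | Section |
|---|---|---|
| Consent and eligibility | Visit 1 | Visit 1: Screening Outpatient Visit |
| Enrolment | Before the run-in: run-in risk is said to be limited by whom the trial enrols (HbA1c <9%) | Risk associated with drug-free run-in period |
| Run-in, by participants already called eligible | Between Visits 1 and 2 | Précis; Study Design |
| Run-in failures leave the study, so had entered it | Run-in | Education and Blood glucose monitoring |
| Baseline tracer | Visit 2 | Visit 2: Baseline Tracer Inpatient Visit |
| Start of drug and first dispensing | Day 2 / end of Visit 2 | Study Agents/ Intervention; Dispensing |
| Randomisation | On entry, once eligible and enrolled; no visit named | Randomization |

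Both conditions of the trigger are met before the run-in. Followed literally, the text assigns the arm then. This is an inference from several sections, not a stated sequence.

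**Step 2: the plan's own figures.** Inputs from Sample Size Justification: difference 0.24, SD of change 0.20, two-sided alpha 0.05, 12 per group, 25% attrition.

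- Standardised difference: 0.24 / 0.20 = 1.2.
- Two-sample t-test, 12 per group: power 0.802; required n 11.94, so 12.
- Recruitment: 12 / (1 − 0.25) = 16 per group. Allowance: 16 − 12 = 4 per group.

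The stated figures reproduce.

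**Step 3: what run-in failures would cost under early assignment.** The documents give no run-in failure rate r and do not split the 25% between run-in and later loss. I assume r = 5-20% and show both readings.

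- Lost per arm before baseline: 16 × r. Share of allowance: 16r / 4.
- *Reading A, the 25% includes run-in loss:* to keep 12 completers, later attrition may be at most 1 − 0.75/(1 − r).
- *Reading B, run-in loss comes on top of 25%:* completers per arm = 16 × (1 − r) × 0.75, with t-test power at that (unrounded) number.

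| r (assumed) | Lost per arm | Share of the 4 | A: later attrition at most | B: completers per arm | B: power |
|---|---|---|---|---|---|
| 5% | 0.8 | 20% | 21.1% | 11.4 | 0.78 |
| 10% | 1.6 | 40% | 16.7% | 10.8 | 0.76 |
| 15% | 2.4 | 60% | 11.8% | 10.2 | 0.73 |
| 20% | 3.2 | 80% | 6.3% | 9.6 | 0.70 |

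**Step 4: the same rates under later assignment.** To randomise 32 after the run-in, 32/(1 − r) must enter it: 34, 36, 38 or 40, rounded up. The 25% then covers post-baseline loss only.

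**The case against.** The strongest reply is that the trigger sentence describes rolling, consecutive assignment rather than a date. Randomisation is not among the Visit 1 activities, and several eligibility results come from blood drawn at that visit. The pharmacy dispenses according to the randomisation table, first at the end of Visit 2, which fits assignment at dispensing equally well. The study-design figure, the obvious place for a randomisation point, is not shown in the copy reviewed. This stands in part: the documents do not establish that participants are in fact randomised before the run-in, and a reader who infers that goes further than they allow. It does not rescue the sentence, which can be followed as written to assign at entry.

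Three further inferences are tempting and not supported.

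- *The baseline is biased by knowledge of the arm.* That needs both early assignment and early disclosure, and no passage says that the pharmacy discloses the arm before dispensing. The primary measure is an isotope enrichment obtained under a standardised inpatient protocol and assayed on coded samples. Bias in it is unlikely; withdrawal decisions and behaviour in the run-in are the more plausible routes.
- *The blocks of 6 are broken.* Losses after assignment may unbalance the completers, as any dropout does. The allocation itself stays valid.
- *The sample size is wrong.* It reproduces. The 25% is applied to those recruited and may reasonably be read as already covering run-in losses.

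The 5-20% range is also an assumption. The short run-in, the HbA1c limit and daily review may keep the true rate low.

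**Conclusion.** The point holds as a weakness in the stated trigger, conditional on the order of events. The only timing rule most naturally places assignment before the run-in and baseline tracer; no passage confirms or excludes this. If it is followed that way, run-in withdrawals are randomised participants who cannot contribute to the primary analysis. At an assumed 5-20% failure they use 0.8 to 3.2 of the 4 per arm allowed for attrition. If such loss is additional to the 25%, power falls from 0.80 to between 0.78 and 0.70; if it is included, 80% power survives only with correspondingly lower later attrition.

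If the arm stays undisclosed until dispensing, these exclusions mainly cost numbers. If it is disclosed on assignment, selective withdrawal becomes possible, and in arms of 16 a few such losses matter. The documents do not settle which applies. The change is worth making because early assignment serves no purpose stated in the protocol and the alternative costs little.

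**What to change.** Reword the trigger in the Randomization section so that the pharmacy is notified, and assigns the arm, only once the Visit 2 tracer study is complete and before the first supply is dispensed. Report run-in withdrawals as pre-randomisation losses, separately from attrition after assignment.

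Cost: one sentence and a line in the participant flow. The pharmacy must assign and dispense on the same day, after a tracer that ends at 2pm and possibly on a weekend or holiday, since such visits are offered. It already dispenses at the end of Visit 2, so the added step is the assignment.

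If the sponsor also wants 32 randomised at that later point, about 34-40 must enter the run-in at the assumed 5-20% failure, from the roughly 60-70 eligible youth estimated at the referral clinic. That is a separate choice: the timing change does not depend on it. If 32 remains the number entering, the protocol should say that the 25% covers run-in loss as well. No dose or clinical withdrawal rule needs to change for this.

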Interestingly, only 3 of the 120 articles measured “therapeutic” metformin concentrations defined as trough concentrations 12 hours after drug administration and during continual therapy. This is in contrast to the multiple articles that cite maximum concentration (Cmax) as the pharmacokinetic parameter of interest. Therefore, establishing a database or algorithm to define more accurately the therapeutic window of metformin, especially in adolescents is urgently needed. To our knowledge there is only one database of metformin plasma concentrations which was collected from 467 adult patients in France⁵⁶. Mean metformin concentrations were 2.7+/-7.3mg/L with range in plasma levels between 0-61mg/L. This range is markedly greater than the currently published toxic levels of 45mg/L assigned by the International Association of Forensic Toxicologists.

We will assess metformin pharmacokinetics in youth with type 2 diabetes who are receiving metformin daily for 3 months. This information will be used to construct a pharmacokinetic-pharmacodynamic model that may be useful for elucidating mechanisms of metformin responsiveness and non-responsiveness in youth and identifying target drug exposures in this population.

Combination therapy of metformin and liraglutide

Combination therapy is likely to be an ideal therapeutic strategy to address the accelerated trajectory towards metabolic decompensation in youth with type 2 diabetes⁵⁷. We propose that a combination regimen of metformin and liraglutide will be complementary in their glucose lowering effect because of their individual ability to lower gluconeogenesis and enhance the incretin response. This proposal will directly test this hypothesis by comparing African-American youth on combination therapy with metformin and liraglutide to youth treated with metformin alone under basal fasting conditions and during meal absorption.

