a. Admission, OGTT and DXA scan

Youth will be admitted in the morning (~7am) on Day 1 and blood samples for hormones, genetic analysis, inflammatory markers and metabolites (including glucose, insulin, C-peptide, glucagon, and isotopic enrichments of glucose, glycerol and body water) will be collected at baseline. One intravenous catheter will be placed in the arm for blood draws. Blood and urine collection for genetic samples for future analysis will occur on admission for Visit 2 only.

- Oral Glucose Tolerance Test (OGTT)

Youth will undergo a 75gram oral glucose tolerance test with blood samples collection at 0, 15, 30, 60, 90 and 120 minutes for hormones and metabolites (including glucose, insulin, glucagon-like-1 peptide and gastrointestinal inhibitory peptide) and metabolites. To measure blood (plasma and RBC) plasma samples for metformin at baseline, 3ml of blood will be collected at 0-time point.

- DXA Scan

Dual x-ray absorptiometry scan will be performed during admission Day 1 to evaluate body composition and determine fat mass and lean body mass.

After the OGTT, youth will eat a standard breakfast, a lunch meal (~1pm) and a snack (~3pm) to provide ~20%, 30% and 10% of total energy needs respectively. Youth will eat a standard dinner meal at ~ 6pm to provide 40% of total energy needs (50% carbohydrate, 33% fat and 17% protein). Total energy expenditure will be estimated from the Mifflin St. Jeor equation ⁶⁹ with a standardized activity factor. Youth will then be placed NPO at 8pm with ad libitum access to water. Another intravenous catheter will be placed in the evening of Day 1, such that the participant will have two intravenous catheters placed, one in each forearm, for stable isotope infusion and blood draws.

On the first day of admission youth will be asked to review their 3 day food records that they recorded prior to admission with a member of the nutrition team. If youth do not bring these records to this appointment, the nutrition team will perform a 24-hour recall to capture the foods consumed the day prior to admission. This will help the investigators to identify if there are differences in dietary intake prior to admission that may impact the results of the testing. The nutrition staff will also obtain body circumference measures, such as neck, waist and hip circumference. These measurements will be done over minimal clothing with a non-stretch measuring tape.

b. Stable isotope administration and steady state labs

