Samples will be processed for isolation of plasma and RBC and frozen at -80C until analysis. Both plasma and RBCs will be processed in duplicate cryotubes (800 – 1000 µl per cryotube for each time-point collected). Cryotubes will be labeled with participant ID and sample time collection and the timing of metformin administration documented. Metformin is stable under refrigerated conditions for up to 24 hours after collection- therefore samples may be kept in the fridge for pickup and processing the next day (the later PK time points- 8 and 12 hours). Analysis for metformin concentration will be via a validated LC-MS/MS assay.

Collection and Storage of Human Specimens or Data

Research Use, Storage and Disposition of Human Subjects' Samples

For future reference and potential use, we will store all samples (blood or fluids) in our locked freezers for an unlimited period of time. Samples will be labeled with coded identifiers linked to patient identity only via a secured database.

Research records and data with personal identifiers will be stored in our locked offices, the medical record department, and the electronic study database. This material will additionally be protected by medical record and computer access procedures. Access to records and data associated with personal information will be restricted to the Principal Investigator, Co-Investigators, study support staff, and database support staff.

Subjects may request that unused samples be removed from our freezers and be destroyed. If no such request is made, we will keep samples until they are completely used or no longer of scientific value, at which time they will be destroyed. We do not plan to destroy personal medical information or stored data. The Principal Investigator will report loss or destruction of data or samples to the IRB.

Genomic Data Sharing Plan

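### Visit 5 gives the last metformin dose at supper (about 6pm) but labels the 8pm sample as taken before that dose; staff cannot follow both

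*Combined protocol and SAP*

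**What the plan says.** The section on Visit 5 (Final Tracer Study) contains both instructions. On dosing it says: "Participants will receive their last dose of study medication at supper in the evening of admission Day 1 during Visit 5". On metformin sampling it lists a Day 1 series running from time 0 of the OGTT to "8h and 8pm (pre-second dose", followed by "Day 2 at 8am and at 2pm".

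That section also makes Visit 5 identical to Visit 2 apart from the extra metformin samples. The Visit 2 section on admission, OGTT and DXA supplies the clock times: "Youth will eat a standard dinner meal at ~ 6pm" and "Youth will then be placed NPO at 8pm", with water still allowed. Table 3 sets the metformin target at 1000 mg twice daily.

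Three other places bear on the point:

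- The laboratory section on Metformin Pharmacokinetics refers to "the later PK time points- 8 and 12 hours" and requires "the timing of metformin administration documented".
- The background section on metformin response and pharmacokinetics defines a therapeutic level as "trough concentrations 12 hours after drug administration and during continual therapy" and notes that only 3 of 120 articles measured it.
- The analysis section on Metformin Pharmacokinetics plans non-linear mixed-effects modelling.

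**The concern.** The Day 1 evening dose is the second metformin dose of that day and also the last of the study. One line puts it at supper. Another requires it to come after an 8pm draw, when supper is over and the fast is starting. The 12-hour point in the laboratory section suggests that the 8pm draw was meant to come 12 h after a morning dose, just before the next one. A ward that follows the supper line will instead draw during absorption of the evening dose.

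The practical risk is inconsistency. If some participants are dosed at supper and others after the draw, a single nominal time point holds two different quantities, and the times since dose of both Day 2 samples differ between participants by about 2 h. Only the exploratory pharmacokinetic-pharmacodynamic aim uses these samples in this way.

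**Working it through.** The plan states no figure to reproduce. The check is clock arithmetic, followed by an illustration of scale.

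**Inputs from the protocol.** Supper at about 6pm and fasting from 8pm (Visit 2 schedule, carried to Visit 5); metformin samples at 8pm on Day 1 and at 8am and 2pm on Day 2 (Visit 5); fasting tracer window opening at 8:30am (stable isotope section); plasma half-life 4–6 h and erythrocyte half-life 18 h (section on risks of the drug-free run-in).

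**Step 1: time since the evening dose.**

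| Event | Dose at supper (~6pm) | Dose right after the 8pm draw |
|---|---|---|
| 8pm sample | ~2 h after | just before |
| Day 2, 8am sample | ~14 h | 12 h |
| Day 2, 2pm sample | ~20 h | 18 h |
| Tracer window opens, 8:30am | ~14.5 h | 12.5 h |

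The 6pm time is approximate, but fasting from 8pm rules out a supper that follows the 8pm draw.

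**Step 2: scale in plasma (illustrative).** Assumptions that are not in the protocol: one compartment, absorption rate ka of 0.4 or 1.0 per hour, 12-hourly dosing to steady state, and the Day 1 first dose at 8am (time 0). With k = ln 2 / half-life, one dose gives, in relative units,

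C(t) = ka/(ka − k) × [exp(−kt) − exp(−ka·t)].

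Let P(t) be the sum of C(t + 12n) over n = 0, 1, 2, …, that is, the level from the 8am dose and all earlier ones, t hours after 8am.

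- 8pm level, supper dose versus dose held: [P(12) + C(2)] / P(12)
- Day 2 8am level, 6pm versus 8pm dose: [P(24) + C(14)] / [P(24) + C(12)]
- Day 2 2pm level, 6pm versus 8pm dose: [P(30) + C(20)] / [P(30) + C(18)]
- Pre-supper versus 12 h level: P(10) / P(12)

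Worked case, half-life 4 h and ka = 1.0: k = 0.1733, C(2) = 1.2096 × (0.7071 − 0.1353) = 0.692, P(12) = 0.173, so the 8pm ratio is 1 + 0.692/0.173 = 5.0.

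| Half-life, ka | 8pm ratio | Day 2 8am ratio | Day 2 2pm ratio | 10 h / 12 h |
|---|---|---|---|---|
| 4 h, 0.4 | 2.92 | 0.762 | 0.748 | 1.36 |
| 4 h, 1.0 | 5.00 | 0.744 | 0.744 | 1.41 |
| 6 h, 0.4 | 2.06 | 0.855 | 0.847 | 1.24 |
| 6 h, 1.0 | 2.98 | 0.845 | 0.845 | 1.26 |

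So the 8pm plasma level is about 2.1 to 5.0 times the pre-dose level, and the Day 2 levels are about 15% to 26% lower than after an 8pm dose.

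**Step 3: what remains recoverable.** Under supper dosing, the slope between the two Day 2 samples is 0.169 and 0.173 per hour (true value 0.173) at a 4 h half-life, and 0.114 and 0.116 (true value 0.116) at 6 h. Elimination is still estimable. In the same model the time-0 level equals the 12 h level by construction.

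**Step 4: red cells.** With the 18 h half-life, 2 h of simple elimination is 1 − 2^(−2/18) = 7%. The plasma shifts in Step 2 therefore do not carry over to the erythrocyte samples.

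**The case against.** The best case for leaving the text alone is that this is a matter of wording. The section on Visit 5 gives no clock time for supper; 6pm is approximate and comes from Visit 2. The supper sentence could be meant only to identify which dose is last, with the sampling line fixing the time. Water is allowed after 8pm, so a tablet straight after the draw is feasible. The last point stands and supports the fix. The reading itself does not: the sentence places the dose at supper, covers study medication without exception, and applies to an arm in which metformin is the only drug.

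The objection that the harm is small stands. Dose timing must be documented, and a mixed-effects model can use a sample about 2 h after a dose. The sequence of sample times implies that the first dose is given at time 0, although the text does not say so. If so, the time-0 sample is probably itself a trough about 12 h after the previous evening's dose. The 12-hour trough is discussed as background and is not a listed outcome.

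Two stronger inferences are therefore unsupported. A reader might conclude that the study loses its only on-treatment trough; the time-0 sample makes that unlikely. A reader might also expect a biased exposure area over the dosing interval; the plan names software suited to non-compartmental analysis but defines no such area as an outcome.

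**Conclusion.** The contradiction is real and the plan does not resolve it. It is minor. Following the supper line moves the 8pm sample from just before the dose to about 2 h after it, and the Day 2 samples from 12 h and 18 h to about 14 h and 20 h. Inconsistent practice would mix the two across up to 32 participants, or 24 if the assumed 25% attrition occurs (32 × 0.75).

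The clock times rest only on the protocol, with supper at about 6pm carried over from Visit 2. The plasma ratios are illustrative and depend on the assumed absorption rate, the 8am first dose and steady state. They show that the two readings of the 8pm sample are different quantities; they do not estimate an error in a planned result.

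A reader might infer that the gluconeogenesis comparison is also compromised, because the evening dose time sets the interval to the fasting tracer window. The documents do not support that. The interval differs by about 2 h between the two readings, either rule would apply to both arms, and nothing in the protocol indicates an effect of that difference on the measurement. The sample size and the primary analysis are untouched.

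**What to change.** State one evening metformin time for all participants in the section on Visit 5.

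**Option that keeps the 12-hour point.** Give the evening metformin dose with water right after the 8pm draw, and amend the supper instruction for metformin. The 8pm sample is then truly pre-dose, and the Day 2 samples fall at 12 h and 18 h. This fits the laboratory section as written. The costs are a dose taken apart from the meal and about 2 h less between dose and fasting tracer window (12.5 h instead of about 14.5 h) in both arms.

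**Option if the supper dose must stay.** Move the 8pm draw to just before supper, label it pre-dose at about 10 h, label the Day 2 samples about 14 h and 20 h, and amend the 12-hour point in the laboratory section. Dosing and the tracer interval do not change. The cost is a 10 h level, about 1.2 to 1.4 times the 12 h level on the illustrative model, and the loss of the 8pm sample's information on the second dose.

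Under either option, say whether the first dose of Day 1 is given at time 0, and analyse by recorded dose and sample times. No samples are added. The first option edits one section and the second edits two.
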